### 2.1.1. Primary Estimand(s)

The primary estimands of this study will use the treatment policy strategy and estimate the treatment difference without the benefit of additional prohibited medications during treatment and regardless of participant compliance with the IP dosing. This estimand (Estimand 1) for AD and Psoriasis are defined according to the primary objectives and are in alignment with the primary endpoints.

For AD, it includes the following 4 attributes:

- Population: Participants with mild or moderate AD as defined by the inclusion and exclusion criteria; without the benefit of receiving prohibited medications during treatment and regardless of compliance.
- Variable: Percent change from baseline in EASI total score at Week 6.
- Intercurrent event(s): A) Prohibited medication – all scores in participants who receive prohibited medication post randomization will be omitted from the analysis and treated as missing scores. Missing scores will be imputed based on the assumption that participants do not benefit from the IP treatment. B) Withdrawal and all other events leading to missing data will be treated similarly assuming participants have efficacy values similar to control participants. C) Inadequate compliance – participants data will be used as recorded.
- Population-level summary: The percent change from baseline mean difference between treated and vehicle in EASI score.

For Psoriasis, it includes:

- Population: Patients with mild to moderate plaque psoriasis as defined by the inclusion and exclusion criteria of the study who do not take prohibited medications during treatment and regardless of compliance.
- Variable: Change from baseline PASI score at Week 6.
- Intercurrent events: A) Prohibited medication – all scores in participants who receive prohibited medication post randomization will be omitted from the analysis and treated as missing scores. Missing scores will be imputed based on the assumption that participants do not benefit from the IP treatment. B) Withdrawal and all other events leading to missing data will be treated similarly as in A). C) Inadequate compliance – participants data will be used as recorded.
- Population-level summary: The mean difference between treated and vehicle control arms of the change from baseline PASI score.

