6.7. Intervention After the End of the Study

No intervention will be provided to study participants at the end of the study.

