9.1. Estimands and Statistical Hypotheses

9.1.1. Estimands for AD

The primary estimand will be the population average treatment effect on percent change from baseline in EASI score relative to vehicle at 6 weeks in the absence of prohibited medication without regard to compliance. All observations after the initiation of prohibited medication will be set to missing. Missing data from all causes, including post-randomization prohibited medication use will be imputed in the PF-07038124 arms using a copy to control method (ie, missing data in 0.01% QD regimen will be imputed from the distribution of participants on QD vehicle). Participants with inadequate compliance will have their recorded EASI scores used as is in the analysis. The population-based treatment effect will be the differences in the mean change from baseline in treatment arm compared to the vehicle.

The secondary estimand will be the estimated population average treatment effect on the rates of IGA response (participants with a score of 0 or 1 and a 2 point or greater decrease from baseline) at Week 6 relative to vehicle without regard to compliance with IP in the absence of prohibited medication. This is a composite estimand where success is defined as achievement of an IGA response as defined above while remaining on study, providing data and not taking prohibited medication; lack of compliance or adverse events will not be counted as a failure. The population-based treatment effect will be the differences in the proportions of success in each treatment arm compared to the corresponding vehicle. EASI 75 and other EASI scores will be treated in a similar manner.

All other secondary continuous clinical endpoints will be analyzed using the primary estimand, while all other secondary categorical clinical endpoints will be analyzed using the secondary estimand described above. CCI

Other estimands may be used for some of the primary and secondary endpoints as a means to examine the robustness of the results and to compare to available literature as needed. Details of these analyses will be presented in the Statistical Analysis Plan (SAP).

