9.1.2. Estimands for Psoriasis

The primary estimand will be the population average treatment effect on change from baseline in PASI scores at Week 6 relative to vehicle without regard to compliance in the absence of prohibited medication. Measurements after the initiation of prohibited medication will be censored and treated as missing data. Missing data due to censoring, study withdrawal or other reasons will have data imputed using a copy to control method (ie, missing data in 0.01% QD regimen will be imputed from the distribution of participants on QD vehicle) assuming these participants no longer receive an efficacy benefit from the IP but rather, have a response similar to participants assigned to vehicle. Participants with inadequate compliance will have their recorded PASI scores used as is in the analysis. The population-based treatment effect will be the differences in the mean change from baseline in each treatment arm compared to the corresponding vehicle.

The secondary estimand will be the population average treatment effect on the PGA response rate (percentage of participants with a score of clear (0) or almost clear (1) and ≥ 2 point improvement from baseline at Week 6 relative to vehicle without regard to compliance with IP in the absence of prohibited medication. This is a composite estimand where success is defined as achievement of a PGA response while remaining on study, providing data and not taking prohibited medication; lack of compliance or adverse events will not be counted as a failure. The population-based treatment effect will be the differences in the proportions of successes in each treatment arm compared to the corresponding vehicle.

All other key secondary continuous clinical endpoints will be analyzed using the primary estimand, while all other key secondary categorical clinical endpoints will be analyzed using the secondary estimand described above. CCI

Other estimands may be used for some of the primary and secondary endpoints as a means to examine the robustness of the results and to compare to available literature as needed. Details of these analyses will be presented in the SAP.

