### 2.1.2. Secondary Estimand(s)

Estimand E2: This estimand is intended to provide a population level estimate of the treatment effect of the IP on a binary responder endpoint; without the benefit of additional prohibited medications and regardless of a participant compliance with the IP dosing.

All continuous secondary endpoints will be analyzed descriptively and using estimand E1 described above, when appropriate.

All binary secondary endpoints will be analyzed descriptively and using estimand E2 described above, when appropriate.

- Population: Participants with mild or moderate AD or Psoriasis as defined by the inclusion and exclusion criteria; without the benefit of receiving prohibited medications during treatment and regardless of compliance.
- Variables: Proportion of participants achieving IGA score of clear (0) or almost clear (1) and a reduction from baseline of  $\geq 2$  points at Week 6 for AD; Proportion of participants with PGA score clear (0) or almost clear (1) (on a 5-point scale) and  $\geq 2$  points improvement from baseline at Week 6 for Psoriasis; and other categorical secondary endpoints.
- Inter-current Events: A) Prohibited medication – response will be considered negative for participants who receive prohibited medication post-randomization. B) Withdrawal and all other events leading to missing data will be treated similarly assuming that participants no longer receive benefit from the IP and hence will be treated as failure for endpoint above. C) Inadequate compliance – participants data will be used as recorded.
- Population level summary:

The difference in proportions between IP treated and vehicle response rates.

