## **5.3. Methods to Manage Missing Data**

### **5.3.1. Efficacy Data**

The primary analysis will use the primary estimand continuous endpoint set. For each landmark analysis (eg, cross sectional analysis by week) missing data, except missing due to COVID-19 pandemic, will be imputed using a control based imputation method. PROC

MI will first be called at the visit and a control based method (implemented with the MNAR option) will impute missing vehicle observations under the assumption data are missing at random (MAR) and impute missing treatment observations assuming they are similar to corresponding vehicle patients.

Summaries of continuous data will use the observed data only and no additional considerations are needed.

Analysis of binary data will use the Secondary Estimand Categorical Endpoint Set. This dataset by definition has no missing data since all missing values, except missing due to COVID-19 pandemic, will have been set to a non-responder. Summaries will use the Observed Efficacy Set and will report results on an observed case (OC) basis.

If a subject misses a visit due to COVID-19, he/she will be excluded from the analysis for that visit; If a subject discontinues treatment or withdraws from the study due to COVID-19, he/she will be excluded from the analyses after the treatment discontinuation visit or study withdrawal visit, respectively.

CCI

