##### 6.1.1.1. Main Analysis

- Estimand strategy: Primary Estimand ([Section 2.1.1](#)). This estimand is intended to provide an estimate of the treatment effect in the absence of prohibited medication use in a population that may or may not be fully compliant with the treatment.
- Analysis set: mITT ([Section 4](#)) using data prepared in the description of the full analysis set.
- Analysis methodology: Percent change from baseline will be analyzed using an ANCOVA with the observed (or imputed) Week 6 change from baseline EASI score as the dependent variable with treatment arm and baseline EASI score as the independent variables. Same method will be used for change from baseline PASI score at Week 6.
- Intercurrent events and missing data: Data prohibited medication will be excluded and set to missing. Missing data which will be multiply imputed using a control-based strategy as described in ([Section 5.3](#)). A thousand (1000) imputed datasets will be used in the analysis and results combined using PROC MIANALYZE.
- The least-squares (LS) means, the 90% confidence interval for the LS means, the difference between the LS means for each pair of treatment groups, and the corresponding 90% confidence interval will be presented.

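### SAP 2.1.1 removes every score of a participant who uses prohibited medication after randomisation, whereas the protocol removes only scores taken after that use began; the SAP rule should be given the protocol's time order.

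*SAP*

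**What the plan says.** The protocol orders the rule in time. For atopic dermatitis, Protocol 9.1.1 says "All observations after the initiation of prohibited medication will be set to missing". For psoriasis, Protocol 9.1.2 says "Measurements after the initiation of prohibited medication will be censored and treated as missing data". The analysis tables in Protocol 9.4.1 and 9.4.2 likewise tie censoring to the start of prohibited medication.

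SAP 2.1.1 states the E1 rule once for each indication in the same words: "all scores in participants who receive prohibited medication post randomization will be omitted from the analysis and treated as missing scores". The unit is now the participant rather than the observation, and the only timing given is that use follows randomisation. The same section describes the estimand as "without the benefit of additional prohibited medications during treatment and regardless of participant compliance with the IP dosing".

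SAP 6.1.1.1 and 6.2.3.1 say only "Data prohibited medication will be excluded and set to missing", where a word or phrase appears to be missing. SAP 5.3.1 then tells the analyst to "impute missing treatment observations assuming they are similar to corresponding vehicle patients".

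For the binary estimand (E2), SAP 2.1.2 says "response will be considered negative for participants who receive prohibited medication post-randomization".

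**The concern.** SAP 2.1.1 is the only complete statement of the E1 rule that a programmer has. SAP 5.3.1 gives no timing, 6.1.1.1 and 6.2.3.1 are incomplete, and the sample code in Appendix 4 contains no censoring step. Programmed as worded, the rule throws away scores that the protocol keeps.

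Two things are at stake. First, a participant who starts prohibited medication late in treatment would lose the earlier, uncontaminated visits. Second, follow-up is also after randomisation. Protocol 5.3.3 bars topical treatments on IP-treated skin for the whole study, and concomitant treatments are recorded at the follow-up visit. On the widest reading, a first use in follow-up would therefore delete a Week 6 EASI or PASI score obtained before it, and in the active arm a vehicle-like value would replace it.

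**Working it through.** **1. The rules applied to three cases** (post-baseline visits at Weeks 1, 2, 4 and 6)

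| First prohibited use | Protocol, E1 | SAP 2.1.1 wording, on-treatment use only | SAP 2.1.1 wording, any use after randomisation |
|---|---|---|---|
| Between Weeks 2 and 4 | Keeps Weeks 1, 2; removes 4, 6 | Removes 1, 2, 4, 6 | Removes 1, 2, 4, 6 |
| Between Weeks 4 and 6 | Keeps Weeks 1, 2, 4; removes 6 | Removes 1, 2, 4, 6 | Removes 1, 2, 4, 6 |
| After the Week 6 assessment, in follow-up | Keeps Weeks 1 to 6 | Keeps Weeks 1 to 6 | Removes 1, 2, 4, 6 |

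In the first two rows Week 6 is missing under both documents. The sample code in SAP Appendix 4 imputes Week 6 from baseline alone, so losing Weeks 1 to 4 would not alter the primary ANCOVA. It would alter the by-visit E1 summaries and the MMRM, which uses observed data and would lose that participant altogether. Only the last row, on the widest reading, touches the primary endpoint.

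**2. The plan's own power figures**

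Inputs from Protocol 9.2.1 and 9.2.2:
- AD: difference 50, SD 48, 21 evaluable per arm, two-sided 0.05.
- Psoriasis: difference 4.5, SD 4.2, 12 evaluable per arm, two-sided 0.10.

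Two-sample t-test power (noncentral t) is 90.9% for AD (stated: approximately 90%) and 81.5% for psoriasis (stated: approximately 80%). Both reproduce.

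**3. Illustration of a Week 6 effect**

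The share f is an assumption; the documents give no rate. Let f be the share of active-arm Week 6 scores erased, unrelated to outcome, and replaced by vehicle-like values. Erased vehicle scores are imputed from the vehicle arm, so the expected vehicle mean does not move.

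- Active mean = (1-f) × active + f × vehicle, so the difference = (1-f) × planned difference.
- Active variance = SD² + f(1-f) × difference².
- Example, AD at f = 10%: difference 0.9 × 50 = 45; active variance 48² + 0.09 × 50² = 2304 + 225 = 2529; pooled SD = √((2529 + 2304)/2) = 49.16.

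| f | EASI difference | AD power | PASI difference | Psoriasis power |
|---|---|---|---|---|
| 0 | 50 | 90.9% | 4.5 | 81.5% |
| 5% | 47.5 | 87.1% | 4.28 | 77.0% |
| 10% | 45 | 82.5% | 4.05 | 72.1% |
| 20% | 40 | 71.5% | 3.60 | 61.9% |
| 30% | 35 | 58.9% | 3.15 | 51.5% |

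**4. Sensitivity of the illustration**

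A simulation with 21 per arm erased 2, 4 or 6 scores in each arm and imputed them from vehicle, without a baseline covariate. Erasing at random gave mean differences of 45.1, 40.3 and 35.7, with power of about 81%, 66% and 49%. Erasing the poorest outcomes in both arms gave 45.3, 40.3 and 35.1, with power of about 88%, 84% and 77%. The shrinkage in the mean was similar in these two cases. The power depends strongly on who is affected, so the power columns in step 3 are indicative only.

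**The case against.** The best defence is that SAP 2.1.1 already confines the event to the treatment period, in its opening description and in the population attribute for each indication, and that SAP 2.1.2 does the same for E2. The last dose is applied at the Week 6 visit (Protocol 6.1.1.1), so medication first used in follow-up is not naturally an intercurrent event for a Week 6 variable. Nor can the words about all scores be meant literally, since they would also remove the Day 1 baseline that the ANCOVA and the imputation need. Both documents say that major changes to the primary analysis would appear in a protocol amendment, and the protocol still censors from initiation. All this suggests loose drafting rather than a new rule.

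Much of that stands. A reader might infer that the SAP will erase valid Week 6 results whenever therapy restarts in follow-up. The documents do not establish this, because the treatment-period framing supports a narrower reading. A reader might also infer that such restarts are likely. No passage says so or gives a rate, and Protocol 5.3.3 forbids topical treatment of those areas throughout the study. The statement in Protocol 6.7 that "No intervention will be provided to study participants at the end of the study" concerns what happens after the study and is no evidence about medication use in follow-up.

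A third tempting inference is that the E2 rule also contradicts the protocol. It does not. Protocol 9.1.1 and 9.1.2 define response as a composite that includes not taking prohibited medication, with no explicit time limit.

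The defence does not reach the loss of pre-initiation scores at Weeks 1 to 4. Nor does it remove the mismatch, within SAP 2.1.1, between a treatment-period estimand and an event rule dated only from randomisation.

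**Conclusion.** The E1 rule in SAP 2.1.1 is over-broad. It conflicts with Protocol 9.1.1, 9.1.2, 9.4.1 and 9.4.2 and sits badly with the SAP's own framing. Followed literally, it drops valid scores taken before first use: at Weeks 1 to 4 on any reading, and at Week 6 only if follow-up use counts.

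On the narrower reading the primary result is unaffected. On the wider reading the expected Week 6 difference shrinks by (1-f) under the assumptions in step 3. Because f is unknown, and f = 0 gives no effect, no bias in the primary endpoint has been shown. The planned sample size and power need no correction. For E2 the missing time limit is an ambiguity shared with the protocol, not a discrepancy between the documents.

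**What to change.** - **SAP 2.1.1, both indications:** state that only scores collected after the first use of prohibited medication are set to missing, and that earlier scores are kept, including a Week 6 score taken before first use.
- **SAP 6.1.1.1 and 6.2.3.1:** complete the broken sentence in the same words.
- **SAP 2.1.2:** clarify that non-response applies to visits after first use, so use that first occurs after the Week 6 assessment does not change Week 6 response. Present this as a clarification, because the protocol's E2 definition has no explicit time limit.

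The cost is about one sentence in each place, settled before the database is released. Protocol 6.5 already requires start dates for concomitant medications, so no new data are needed. A short convention for use that starts on a visit day would complete the rule. Sample size, alpha and trial conduct stay as they are.

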### 2.1.2. Secondary Estimand(s)

Estimand E2: This estimand is intended to provide a population level estimate of the treatment effect of the IP on a binary responder endpoint; without the benefit of additional prohibited medications and regardless of a participant compliance with the IP dosing.

All continuous secondary endpoints will be analyzed descriptively and using estimand E1 described above, when appropriate.

All binary secondary endpoints will be analyzed descriptively and using estimand E2 described above, when appropriate.

- Population: Participants with mild or moderate AD or Psoriasis as defined by the inclusion and exclusion criteria; without the benefit of receiving prohibited medications during treatment and regardless of compliance.
- Variables: Proportion of participants achieving IGA score of clear (0) or almost clear (1) and a reduction from baseline of  $\geq 2$  points at Week 6 for AD; Proportion of participants with PGA score clear (0) or almost clear (1) (on a 5-point scale) and  $\geq 2$  points improvement from baseline at Week 6 for Psoriasis; and other categorical secondary endpoints.
- Inter-current Events: A) Prohibited medication – response will be considered negative for participants who receive prohibited medication post-randomization. B) Withdrawal and all other events leading to missing data will be treated similarly assuming that participants no longer receive benefit from the IP and hence will be treated as failure for endpoint above. C) Inadequate compliance – participants data will be used as recorded.
- Population level summary:

The difference in proportions between IP treated and vehicle response rates.

### 2.1.3. Additional Estimand(s)

There is no defined estimand for other endpoints, and they will be analyzed using Pfizer data standards as applicable.

## 2.2. Study Design

*This is a phase 2a, randomized, double blind, vehicle controlled, parallel group, multicenter study on the efficacy, safety, tolerability and PK of PF-07038124 0.01% QD versus vehicle control in the treatment of adult participants with mild to moderate AD or mild to moderate plaque psoriasis. In this study the efficacy of PF-07038124 ointment versus vehicle will be assessed in two different indications – there is a separate vehicle control group for each indication.*

[figure not shown]
*A total of approximately 88 participants with AD or psoriasis will be randomly assigned to study intervention in this basket trial design.*

*For AD, a maximum of approximately 56 participants will be randomly assigned to study intervention such that approximately 42 evaluable participants complete the study. Assuming a 25% drop out rate, approximately 28 participants will be randomized to either PF-07038124 or vehicle control to achieve approximately 21 completers in each group. Randomization will be stratified by baseline disease severity (mild [Investigator's Global Assessment or IGA = 2] vs. moderate [IGA = 3]). Up to 25% of AD participants will have an IGA score of 2 at baseline.*

*For psoriasis, a maximum of approximately 32 participants will be randomly assigned to study intervention such that approximately 24 evaluable participants complete the study. Assuming a 25% drop out rate, approximately 16 participants will be randomized to PF-07038124 or vehicle control to achieve 12 completers in each group. Randomization will be stratified by baseline disease severity (mild [Physician Global Assessment or PGA = 2] vs. moderate [PGA = 3]). Up to 25% of participants will have a PGA score of 2 at baseline.*

*The total duration of study participation will be approximately 17 weeks, including a screening period of up to 6 weeks, a double-blind, placebo-controlled treatment period of 6 weeks, and a safety follow-up period of 4-5 weeks from last dose of study drug to last study visit. The study intervention arms and duration for AD and psoriasis participants are the same.*

**Figure 1 Study Design Schema**

↑ Primary study endpoints of EASI or PASI will be obtained at Week 6 visit.

### 3. ENDPOINTS AND BASELINE VARIABLES: DEFINITIONS AND CONVENTIONS

#### 3.1. Primary Endpoint(s)

- *Percent change from baseline in EASI total score at Week 6* (see Protocol Section 3.1). The baseline will be defined as the EASI total score on Day 1 predose.

- *Change from baseline in PASI score at Week 6 (see Protocol Section 3.2). The baseline will be defined as PASI score on Day 1 predose.*

